### **9.5.1. Tolerability Analysis**

Injection site reactions will be recorded as adverse events according to the following severity assessment criteria:

- Assessment of injection site erythema, induration, and ecchymosis will be recorded according to measurements: 5 to  $\leq$ 50 mm (mild),  $>$ 50 to  $\leq$ 100 mm (moderate), and  $>$ 100 mm (severe).
- Injection site pain will be recorded using the 11-point numerical rating scale and will be mapped to mild, moderate, or severe, according to participant's self-report of pain intensity, as described for the recording of headache pain in Section 8.2.1.
- Appropriate treatment may be provided if necessary, in which case it must be recorded as concomitant medication.

Tolerability will be assessed by the following:

- the number (%) of participants who fail to complete the trial (day 85, final assessment)
- the number (%) of participants who fail to complete the trial due to adverse events

Local tolerability findings will be listed and summarized descriptively.

## **9.6. Other Analyses**

### **9.6.1. Pharmacokinetic Analysis**

Pharmacokinetic plasma concentration results (fremanezumab) will be tabulated descriptively at each planned sampling time point by weight cutoff.

In addition, the most appropriate population pharmacokinetic model will be developed. This analysis will be reported separately, as appropriate.

### **9.6.2. Pharmacokinetic/Pharmacodynamic Analysis**

The pharmacokinetics/pharmacodynamic relationship may be estimated by compartmental techniques. The pharmacokinetic parameters will be based on fremanezumab measurements. The pharmacodynamic measures will be the efficacy/safety responses.

The pharmacokinetic/pharmacodynamic relationship may be estimated using the most appropriate model after comparing different candidate models for their quality of fit. If performed, this analysis will be reported separately.

### **9.6.3. Immunogenicity Analysis**

Summary of immunogenicity results will be provided, and the incidence of immunogenicity will be calculated. The impact of immunogenicity on the pharmacokinetic profile, drug efficacy, and clinical safety will be evaluated if data allows. This analysis will be reported separately.

## **9.7. Interim Analyses**

There will be no formal interim analysis.

## **9.8. Sample Size Determination**

The sample size planned is approximately 266 participants (133 evaluable participants completing the trial per treatment group). Assuming a treatment difference of 1.7 days (reduction in monthly average number of headache days of at least moderate severity) and a common SD of 4.92, a sample size of 133 participants per treatment group gives at least 80% power for the trial to succeed at an alpha level of 0.05. Assuming a 4% discontinuation rate, approximately 278 participants (139 participants per treatment group) will be randomized. Participants will be randomized to receive either monthly sc administration of test IMP or placebo IMP.

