3.1. Primary and Secondary Trial Objectives and Endpoints	Primary efficacy endpoint was updated from “...headache days of at least moderate severity...” to “...migraine days...”  First 2 secondary efficacy endpoint bullets were updated. Bullet 1: changed from “migraine days” to “headache days of at least moderate severity”. Bullet 2: changed from “headache days of at least moderate severity” to “migraine days”.	Updated to align with other pediatric and adult trials.  Updated to align with other pediatric and adult trials.

Section Number and Name	Description of Change	Brief Rationale
3.1.1. Justification of Primary Endpoint	Aligning with the change to primary endpoint from “headache days” to “migraine days”.	Clarification.
3.2. Primary Estimand	Update text from headache to migraine days: “...number of migraine days during...”	Alignment with objectives.
3.4. Exploratory/Other Objectives and Endpoints	[REDACTED] [REDACTED] [REDACTED] [REDACTED] [REDACTED]	[REDACTED] [REDACTED] [REDACTED]
4.1. Description of Trial Design 4.1.1. Planned Number of Participants and Countries	
Enrollment target was reduced from “approximately 418 patients” to “approximately 278 patients”. The number of evaluable participants is planned to be “approximately 266” based on the currently observed drop-out rate of 4%.
 
In line with the current projections and reduced sample size, trial completion date was updated from “Q4 2023” to “Q3 2026”. Trial start date was updated from Q1 2020 to Q2 2020.
 
Text on interim analysis and/or sample size re-estimation was removed.
	
Mitigation to the observed recruitment constrains and further trial completion delays.
 
Mitigation to the observed recruitment constrains and further trial completion delays.
 
Removed due to recruitment constraints and to avoid further trial completion delays.

4.4 Start of Trial and End of Trial	Suggested template text added that “trial start date is the date on which the clinical trial will be open for recruitment of participants.”	Alignment with new template.
5.3. Inclusion Criteria	
Inclusion criteria c was revised to “...history of <math>\geq 15</math> headache days per month on average during the 3 months...” and inclusion criteria e was deleted.
 
Inclusion criteria f was updated to specify that “approximately 35% of participants” are allowed preventive medications.
	Aid with recruitment.

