	Appendix J in previous version of protocol).	
9. STATISTICAL CONSIDERATIONS	New template text added.	Alignment with new template.
9.1.4. Per Protocol Analysis Set	Updated text to specify this is a subset of the Full Analysis Set.	Clarification.
9.2. Analyses Supporting Primary Objective(s) 9.2.1. Primary Endpoint 9.2.1.1. Estimand for the Primary Endpoint 9.2.2. Secondary Endpoints 9.2.3. Exploratory/Other Endpoints 9.2.4.1. Primary Efficacy Analysis 9.2.4.2. Sensitivity and Supplementary Analyses 9.3. Analysis Supporting Secondary Objective(s)	In all subsections relevant text referring to “headache days of at least moderate severity” or “migraine days” was updated where needed.  Update the definition of migraine day (Section 9.2)	Alignment with updating the primary endpoint.  Alignment with updating the primary endpoint.
9.2.4.1. Primary Efficacy Analysis 9.3. Analysis Supporting Secondary Objective(s)	Added text on weight subgroup analysis.”	Update
9.5. Safety Analyses	Added text on medical device vigilance.	Alignment with new template.
9.6.3. Immunogenicity Analysis	Text updated “...if data allows. This analysis will be reported separately.”	Clarification.
9.7. Interim Analyses	Interim analysis for sample size re-estimation was removed.	Removed due to recruitment constraints and to avoid further trial completion delays.
9.8. Sample Size Determination	Enrollment target was reduced from “approximately 418 patients” to “approximately 278 patients”. The number of evaluable participants is planned to be “approximately 266” based on the currently observed drop-out rate of 4%. Statistical power is consequently reduced from “at least 90% power” to “at least 80%”.  Text on interim analysis and/or sample size re-estimation was removed.	Mitigation to the observed recruitment constraints and further trial completion delays.
10.1. Regulatory and Ethical Considerations	Relocated text on ”Competent Authorities and Independent Ethics Committees/Institutional Review Boards”(in Appendix L of previous version of protocol) to here.	Alignment with new template.

Section Number and Name	Description of Change	Brief Rationale

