### 3.1.1. Justification of Primary Endpoint

This design is consistent with the recommendations of the International Headache Society (IHS) for controlled trials of preventive drugs in migraine ([Tfelt-Hansen et al 2012](#)).

By definition, the IHS diagnostic criteria for CM include patients that suffer  $\geq 15$  headache days per month and/or treat the headache with an acute migraine-specific medication. Headache and migraine days are defined differently in the protocol. This requirement is consistent with migraine preventive treatment guidelines and also with the Teva adult CM trial inclusion criteria.

As per the guidelines for controlled trials of preventive treatment of CM of the IHS, Teva considers that the most appropriate primary endpoint to capture is the change from baseline on the monthly average number of migraine days. Pain is a very subjective experience, and its perception changes among patients. Therefore, it is most important to capture the individual manifestation and perception of migraine in every patient examined. Patients will subjectively rate their headaches as mild, moderate, or severe and record this information using the electronic headache diary device. This endpoint (change from baseline on the monthly average number of migraine days) is a classical endpoint used in most prior studies of CM, and it is recommended by the IHS ([Tfelt-Hansen et al 2012](#)). This is the same primary endpoint used in the adult migraine clinical development program, which showed significant results. Consistent with past trials in CM and the recommendation of the IHS, migraine day or probable migraine day requires meeting the ICHD-3 criteria or days treated with acute migraine therapies (triptans or ergot compounds). Teva will follow these guidelines and recommendations.

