### **9.2.1. Primary Endpoint**

The primary efficacy endpoint is the mean change from baseline (28-day baseline period) in the monthly average number of migraine days during the 12-week period after the first dose of IMP.

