7. MULTIPLE COMPARISONS AND MULTIPLICITY

A fixed-sequence (hierarchical) testing procedure will be implemented to control the Type 1 error rate at 0.05. The sequence of comparisons will be as follows:

1. mean change from baseline (28-day baseline period) in the monthly average number of migraine days during the 12-week period after the first dose of IMP for the TEV-48125 treatment group versus the placebo treatment group
2. mean change from baseline (28-day baseline period) in monthly average number of headache days of at least moderate severity during the 12-week period after the first dose of IMP for the TEV-48125 treatment group versus the placebo treatment group
3. proportion of participants reaching at least 50% reduction in the monthly average number of migraine days during the 12-week period after the first dose of IMP for the TEV-48125 treatment group versus the placebo treatment group
4. mean change from baseline (28-day baseline period) in the monthly average number of days of use of any acute headache medications during the 12-week period after the first dose of IMP for the TEV-48125 treatment group versus the placebo treatment group
5. mean change from baseline (day 1) in migraine-related disability score, as measured by the Pediatric Migraine Disability Assessment (PedMIDAS) questionnaire, at 12 weeks after administration of the first dose of IMP for the TEV-48125 treatment group versus the placebo treatment group
6. mean change from baseline (day 1) in quality of life, as measured by the Pediatric Quality of Life Inventory (PedsQL), at 12 weeks after administration of the first dose of IMP for the TEV-48125 treatment group versus the placebo treatment group

If the resulting 2-sided p-value from the 1st comparison is ≤ 0.05 , then the next comparison of interest will be interpreted inferentially at the alpha level of 0.05. This process will continue either until all comparisons of interest are interpreted inferentially or until the point at which the resulting 2-sided p-value for a comparison of interest is > 0.05 . At the point where $p > 0.05$, no further comparisons will be interpreted inferentially.

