APPENDIX B. LOGICS FOR ENDPOINTS DERIVATION

Migraine day: 1 of the following 3 options				
		OPTION 1		
Part 1	1	A1 / A10	YES	
	2	A2 / A11	YES	
		AND		
		TWO OF THE FOLLOWING		
Part 2	1	A3 / A12	>=4	
	2	A4 / A13	YES	
	3	A5 / A14	YES	
	4	A6 / A15	YES	
		AND		
		ONE OF THE FOLLOWING		
Part 3	1	A7 / A16	YES	
	2	A8 / A17	YES	
		AND		
		A9 / A18	YES	
		OPTION 2		
		1	A1 / A10	YES
		2	B4 / B10	YES
		3	B5 / B11	ERGOT OR TRIPTAN OR NSAID OR PARACETAMOL
			OPTION 3	
		1	A1 / A10	YES
			AND	
			ONE OF THE FOLLOWING	
		1	B1 / B7	YES
		2	B2 / B8	YES

Headache day of at least moderate severity: 1 of the following 2 options			
OPTION 1			
1	A2 / A11	YES	
2	A3 / A12	Moderate (headache severity 4 to 6) or Severe (headache severity 7 to 10)	
OPTION 2			
1	B4 / B10	YES	
2	B5 / B11	ERGOT OR TRIPTAN OR NSAID OR PARACETAMOL	

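### The stated power of at least 80% is for headache days of at least moderate severity, now a secondary endpoint; no power is given for the primary endpoint, migraine days

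*Protocol*

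**What the plan says.** The sample-size paragraph in Protocol 9.8 reads "Assuming a treatment difference of 1.7 days (reduction in monthly average number of headache days of at least moderate severity". It adds a common SD of 4.92 and alpha 0.05, and states power of at least 80% for trial success with 133 evaluable participants per group. A 4% discontinuation rate brings the number randomized to 139 per group, 278 in total. SAP 2.4 carries the same endpoint, difference, SD and numbers.

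Protocol 9.2.1 says "The primary efficacy endpoint is the mean change from baseline (28-day baseline period) in the monthly average number of migraine days". SAP 1.1 agrees, and the first step of the fixed testing sequence in SAP section 7 is the "mean change from baseline (28-day baseline period) in the monthly average number of migraine days during the 12-week period after the first dose". Headache days of at least moderate severity is step 2.

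The Amendment 09 change table explains how this came about. Its entry for Protocol 3.1 begins "Primary efficacy endpoint was updated from" and moves the primary endpoint from headache days of at least moderate severity to migraine days. The entry covering subsections of 9.2 and section 9.3 begins "In all subsections relevant text referring to" and records that the two endpoint names were revised where needed. The entry for 9.8 covers only the enrolment target, drop-out rate, power and removal of interim-analysis text.

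**The concern.** A power figure for trial success should refer to the test that decides success and opens the testing sequence. Here the only stated power belongs to the second test in that sequence. A reader cannot tell whether the primary test was planned with more or less than 80% power, which matters most if the primary result is not significant.

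The inputs cannot be assumed to transfer. Protocol 3.1.1 itself notes: "Headache and migraine days are defined differently in the protocol". A migraine-day count can have a different treatment difference and a different SD from a headache-day count.

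**Working it through.** **1. Reproduce the plan's figure.** Inputs: difference d = 1.7, SD = 4.92, n = 133 per group (Protocol 9.8); 1:1 allocation (Protocol 4.1); two-sided 0.05 (SAP section 7). Method: unadjusted two-sample exact t-test with 2n − 2 degrees of freedom.

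- Standard error = SD × √(2/n) = 4.92 × √(2/133) = 0.6033.
- Noncentrality = d / standard error = 1.7 / 0.6033 = 2.818.
- Degrees of freedom = 264, critical t = 1.969, power = **80.2%**.
- Drop-out: 133 / 0.96 = 138.5, rounded up to 139 per group, 278 in total.

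Both figures match the plan, so the arithmetic is sound for headache days of at least moderate severity.

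**2. Look for the migraine-day inputs.** The protocol and SAP give no migraine-day difference, SD or power, and neither says that 1.7 and 4.92 apply to that endpoint. Power for the primary test therefore cannot be computed from the documents.

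**3. Compare the endpoints.** SAP Appendix B sets out "Migraine day: 1 of the following 3 options" and "Headache day of at least moderate severity: 1 of the following 2 options". They share the acute-medication route, the 2-hour item and the severity item (4 or more), but neither contains the other:

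- An untreated headache of at least 2 hours, severity 5, with no associated symptom or aura, counts only as a headache day.
- An untreated headache of at least 2 hours, severity 3, one-sided and throbbing with nausea, counts only as a migraine day.

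The migraine-day definition also varies between sections. Protocol 9.2 asks for at least one symptom, or use of triptans or ergots. SAP 6.2 adds NSAIDs and paracetamol to the medication route. Appendix B requires several symptoms and adds an aura option.

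**4. See how much the inputs matter.** Same unadjusted t-test:

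| Difference | SD | Power, 133 per group | Power, 139 per group |
|---|---|---|---|
| 1.70 | 4.92 | 80.2% | 81.9% |
| 1.69 | 4.92 | 79.7% | 81.4% |
| 1.70 | 4.95 | 79.7% | 81.4% |

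At 133 per group, 80% power needs a difference of at least 1.697 (with SD 4.92) or an SD of at most 4.93 (with difference 1.7).

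The next values are assumptions, 10% either side of the stated inputs, because the documents give none for migraine days. At 133 per group:

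- SD 4.43 (0.9 × 4.92) gives 87.7%; SD 5.41 (1.1 × 4.92) gives 72.3%.
- Difference 1.53 (0.9 × 1.7) gives 71.5%; difference 1.87 (1.1 × 1.7) gives 87.0%.

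The range lies on both sides of 80%. It shows how far power depends on the inputs, not what the true power was.

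**The case against.** The strongest reply is that this is a leftover label. The 9.8 paragraph speaks of trial success, and the change table does not list 9.8 among the sections where endpoint wording was updated. The sponsor may have meant 1.7 and 4.92 for migraine days. That is possible, but the documents do not settle it, and only the sponsor can confirm it.

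A second reply concerns the margin. The near-misses at 79.7% hold only for an unadjusted t-test at exactly 133 per group. The full analysis set keeps anyone dosed with at least 10 postbaseline diary days, so some of those who discontinue can contribute; at 139 per group both cases give 81.4%. The planned test is an ANCOVA with baseline migraine days as covariate (Protocol 9.2.4.1, SAP 6.2.2). If 4.92 is an unadjusted SD and covariates explain 5%, 10% or 20% of the variance (assumed values), the residual SD is 4.92 × √(1 − share explained) = 4.80, 4.67 or 4.40. Power at 133 per group is then about 82%, 84% or 88%. If 4.92 is already a residual SD, there is no such gain. The documents do not say which it is. This reply stands: a thin margin should not be claimed for the planned analysis.

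Third, the Appendix B comparison uses a later definition. Protocol 9.8 dates from September 2023, and the SAP amendment history records an update of the Appendix B migraine-day derivation in December 2024. Planning values under that derivation may not exist. This also stands and shapes the fix.

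Finally, the analysis has been conducted, according to the note to file, so the sample size cannot change and the confidence interval now carries the information on precision. That limits the consequence but does not correct the statement.

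**Conclusion.** The concern holds as a misattached power statement. The 80% describes headache days of at least moderate severity, and power for the primary endpoint is not documented in either the protocol or the SAP.

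A reader might infer that the trial was underpowered for migraine days. The documents do not support that: they give no migraine-day inputs, and plausible departures go both ways. Nor do they support the opposite inference, that 80% power was secured for the primary test.

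The stated figure itself is correct for its inputs. The power figures here rest on a two-sided 0.05 unadjusted t-test, equal groups and, for the ±10% cases, assumed values. No estimate, p-value or type I error control is affected. The correction should be made, but it is a matter of documentation.

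**What to change.** Correct the power statement, in practice in the CSR: the analysis has been conducted, SAP 2.5.2 requires SAP amendments to be approved before database lock and unblinding, and Protocol 9.9 names the CSR among the places for deviations from the statistical plan. Do one of the following:

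1. Give the design-stage migraine-day difference and SD and their source. Say which migraine-day definition they used (Protocol 9.2, SAP 6.2 or SAP Appendix B) and whether the SD is residual, and give the resulting power at 133 per group.
2. State and justify that 1.7 and 4.92 were meant for migraine days and that the parenthetical in Protocol 9.8 and SAP 2.4 was not updated.
3. Say that the 80% refers to headache days of at least moderate severity and that power for the primary endpoint was not established.

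Do not use power calculated from the observed result. The cost is one paragraph, with no extra participants and no change to any test. The downside is that the stated power for the primary endpoint may become less favourable or have to be reported as not established.

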## **9.9. Protocol Deviations**

Information related to protocol amendments and deviations are provided in Section [11.2](#).

Deviations from the statistical plan, along with the reasons for the deviations, will be described in protocol amendments, the statistical analysis plan, the CSR, or any combination of these, as appropriate, and in accordance with applicable national, local, and regional requirements and regulations.

## **10. GENERAL CONSIDERATIONS: REGULATORY, ETHICAL, AND TRIAL OVERSIGHT**

### **10.1. Regulatory and Ethical Considerations**

#### **Competent Authorities and Independent Ethics Committees/Institutional Review Boards**

Before this trial starts, the protocol will be submitted to the national competent authority and to the respective IRB/IEC for review. As required, the trial will not start at a given investigational center before the IRB/IEC and competent authority (as applicable) for the investigational center give written approval or a favorable opinion.

#### **Compliance Statement**

This trial will be conducted in full accordance with the ICH Harmonised Tripartite Guideline, Guideline for GCP E6, ISO 14155: Clinical investigation of medical devices for human subjects – Good Clinical Practice, and any applicable national and local laws and regulations (eg, Title 21CFR Parts 11, 50, 54, 56, 312, and 314, Directive 2001/20/EC of the European Parliament and of the Council on the approximation of the laws, Regulation [EU] No. 536/2014 [CTR] regulations and administrative provisions of the Member States relating to the implementation of GCP in the conduct of clinical trials on medicinal products for human use). Any episode of noncompliance will be documented.

The Investigator is responsible for performing the clinical trial in accordance with this protocol and the applicable GCP guidelines referenced above for collecting, recording, and reporting the data accurately and properly. Agreement of the Investigator to conduct and administer this clinical trial in accordance with the protocol and applicable regulations will be documented in separate clinical trial agreements with the Sponsor and other forms as required by national competent authorities in the country where each investigational center is located.

The clinical trial agreement shall outline the Investigator's and the institution's responsibilities with respect to the conduct of the clinical trial, including the Investigator's reporting obligation to the Sponsor for suspected cases of serious breach from GCP and/or protocol.

The Investigator is responsible for ensuring the privacy, health, and welfare of the participants during and after the clinical trial; and must ensure that trained personnel are immediately available in the event of a medical emergency. The Investigator and the involved clinical trial personnel must be familiar with the background and requirements of the trial; and with the properties of the IMPs as described in the IB or prescribing information.

The Principal Investigator at each investigational center has the overall responsibility for the conduct and administration of the clinical trial at that/each investigational center and for contacts with trial management, with the IRB/IEC, and with competent authorities.

See Section 10.3 for the ethics expectations of informed consent or assent, Section 10.4 for confidentiality regarding trial participants, Section 13.6 for requirements for registration of the clinical trial, and Section 13.7 for the publication policy.

